4.3 Sample Size

The sample size is not estimated based on powering for any hypothesis testing. There are only approximately 1600 and 40000 Japanese subjects with generalized pustular psoriasis and erythrodermic psoriasis respectively, thus finding subjects to participate in the trial will be difficult. Therefore, the sample size is determined based on feasibility. In total, at least 16 subjects will be enrolled: at least 8 subjects for GPP and EP separately.

4.4 Interim Analysis

An interim analysis will be conducted when the last subject completes the Week 28 visit and all data pertaining to Week 28 and earlier are cleaned. For this analysis all Week 16 efficacy endpoints will be analysed, and all safety as well as pharmacokinetic and antiimmunogenicity data received by cut-off date will be analysed. Another interim analysis will be conducted when the last subject completes the Week 52 visit. The analyses will be performed for the efficacy endpoints until Week 52, as well as all safety and pharmacokinetic and immunogenicity data received by cut-off date.

Additional interim analysis may be performed if deemed necessary for regulatory purpose.

5.0 Analysis Populations

The Intent-to-Treat (ITT) subject population in each Substudy is defined as all randomized subjects with at least one dose of study drug. The Safety population is the same as the ITT population.

5.1 Variables Used for Stratification of Randomization

Subjects who are eligible based on inclusion and exclusion criteria and have had all pre randomization procedures performed will be randomized in a 1:1 fashion in each group to either 150 mg (2 syringes, 75 mg each) or 75 mg (1 syringe) at Week 0, 4 and every 12 weeks. Randomization will be done using an adequate block size.

6.0 Analysis Conventions

Since this is an open-label continuation study, no statistical test will be conducted. Summary statistics will be provided. Data from preceding studies will be integrated with data from this study in the summaries.

Definition of Baseline

For this study, baseline values are defined as the last non-missing values prior to the first dose of study drug in this study. These baseline values will be referred to as "BL" in this document. Unless otherwise specified, this will be the "baseline" for analysis.

Definition of Rx Days (Days Relative to the Date of First Dose of Study Drug)

Rx days are calculated for each time point relative to the date of first dose of this study. They are defined as the number of days between the day of the first dose of risankizumab and the specific time point. Rx days are negative values when the time point of interest is prior to the first risankizumab dose day. Rx days are positive values when the time point of interest is on or after the first risankizumab dose day. The day of the first dose of risankizumab is defined as Rx Day 1, while the day prior to the first risankizumab dose is defined as Rx Day –1 (there is no Rx Day 0).

Definition of Analysis Windows

All time points and corresponding time windows are defined based on Rx Days.

For efficacy analyses, local tolerability, laboratory parameters, and vital sign variables, analysis windows are constructed using the following algorithm:

- Determine the nominal Rx day for each visit (e.g., Week 4 [4 weeks after Baseline visit] equals Rx Day 28).
- In order to include all post baseline data, the first post-baseline interval starts on the first day and the time after the first dose of risankizumab (Rx Day 1).
- Determine the window around a specific nominal Rx day, are presented in the Protocol Appendix C.
- If more than one assessment is included in a time window the assessment closest to the nominal day will be used. If there are two observations equidistant to the nominal day, the one after the nominal day will be used in analyses. If more than one post baseline assessment is included on the same

day, then the worst assessment on that day will be used in analyses, except those specified in Section [11.0](#).

The protocol specified visits and corresponding time windows used in the efficacy analyses, local tolerability, laboratory parameters, and vital sign variables, are presented in the following [Table 1](#) – [Table 32](#).

Table 1. Visit Windows for Analysis of Clinical Laboratory Tests, Vital Signs, Local Tolerability (WBC, CRP and ALB), and Efficacy Variables (PASI/JDA Score and Responder Rating/PGA-GPP/CGI-GI/BSA)

Window Label	Target Day	Interval
Screening	–	[–42, –1]
Baseline ^a	1	≤ 1 ^b
Week 4	29	[2, 43]
Week 8	57	[44, 71]
Week 12	85	[72, 99]
Week 16	113	[100, 134]
Week 22	155	[135, 176]
Week 28	197	[177, 218]
Week 34	239	[219, 260]
Week 40	281	[261, 302]
Week 46	323	[303, 344]
Week 52	365	[345, 407]
Week 64	449	[408, 491]
Week 76	533	[492, 575]
Week 88	617	[576, 659]
Week 100	701	[660, 743]
Week 112	785	[744, 827]
Week 124	869	[828, 911]
Week 136	953	[912, 995]
Week 148	1037	[996, 1079]
Week 160	1121	[1080, 1142]
Week 172	1163	[1143, 1205]
Week 184	1247	[1206, 1261]
Week 188	1275	[1262, 1282]

Rx Day calculated relative to first dose of risankizumab. For subjects randomized but not dosed, Rx Day calculated relative to Randomization.

- a. There is no baseline for local tolerability measurements and CGI-GI.
- b. If time is collected, restrict to records prior to the first dose of study drug.

Table 2. Visit Windows for Analysis of Clinical Laboratory Tests (excluding WBC, CRP and ALB)

Window Label	Target Day	Interval
Screening	–	[–42, –1]
Baseline ^a	1	≤ 1 ^a
Week 8	57	[2, 85]
Week 16	113	[86, 155]
Week 28	197	[156, 239]
Week 40	281	[240, 323]
Week 52	365	[324, 533]
Week 100	701	[534, 869]
Week 148	1037	[870, 1100]
Week 172	1163	[1101, 1205]
Week 184	1247	[1206, 1261]
Week 188	1275	[1262, 1282]

Rx Day calculated relative to first dose of risankizumab. For subjects randomized but not dosed, Rx Day calculated relative to Randomization.

a. If time is collected, restrict to records prior to the first dose of study drug.

Table 32. Visit Windows for Analysis of Efficacy Variable (DLQI)

Window Label	Target Day	Interval
Baseline	1	$\leq 1^a$
Week 12	85	[2, 99]
Week 16	113	[100, 239]
Week 52	365	[240, 407]
Week 64	449	[408, 491]
Week 76	533	[492, 575]
Week 88	617	[576, 659]
Week 100	701	[660, 743]
Week 112	785	[744, 827]
Week 124	869	[828, 911]
Week 136	953	[912, 995]
Week 148	1037	[996, 1079]
Week 160	1121	[1080, 1142]
Week 172	1163	[1143, 1205]
Week 184	1247	[1206, 1261]
Week 188	1275	[1262, 1282]

Rx Day calculated relative to first dose of risakizumab. For subjects randomized but not dosed, Rx Day calculated relative to Randomization.

a. If time is collected, restrict to records prior to the first dose of study drug.

Definition of Missing Data Imputation

The following rules will be used to impute for missing data. Data imputation will be used for missing values in the efficacy analysis, but not the safety analyses.

- For continuous endpoints, LOCF (Last Observation Carried Forward) will be used to impute missing values. The LOCF will use the last observed non-missing evaluation (last completed non-missing evaluation, from composite endpoint) from the previous visit within the particular period for efficacy measures assessed to impute missing data at later visits in the same period. Baseline efficacy evaluations will not be carried forward.
- For all binary endpoints (i.e., endpoints that are either 1 (subject responded) or 0 (subject did not respond):

1. If no assessment after that visit*, then impute as failure (NRI [No Response Imputation])
2. If there are assessments at visits* before and after, only impute as success if both visits are successes; else impute as failure

Subjects that take prohibited medications to treat Psoriasis will be treated the same as those that discontinued from the trial – i.e., subsequent visits following start of prohibited medication will be considered as failure for binary endpoints.

Rounding of Numeric Results

Rounding will be performed for presentation of results. No rounding will be performed before or during analyses. The ROUND function of SAS will be used to round results.

When dichotomizing continuous variables, associated continuous variables will be rounded to 9 decimal points before applying the cutoff point to determine the response status (for example, percent change from baseline in PASI score will be rounded to 9 decimal places before comparing to 90%).

The mean and median will be rounded for presentation to 1 decimal more than the data entered into the database. The standard deviation will be rounded to 2 decimal places more than the data entered into the database. The minimum and maximum values will be presented as entered into the database.

Probabilities will be rounded to 3 decimal places before assignment of statistical significance and will be presented in rounded format. Probabilities that round to zero or are reported by SAS as zero will be presented as "< 0.001." Probabilities that round to 1 or are reported by SAS as 1 will be presented as "> 0.999."

7.0 Demographics, Baseline Characteristics, Medical History, and Previous/Concomitant Medications

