Visits 2, 4, 6, 8, 10, 12, 16, 20, end of treatment (EOT), Week 184 follow-up visit and Week 188 follow-up visit will be performed in fasted state (8 hours no food and only water). If a subject comes in non-fasted where a fasting condition is required, the visit should be performed, the non-fasted condition documented on the laboratory requisition, and the subject reminded about the expected conditions. At Visits 3, 5, 7, 9, 11, 13, 14, 15, 17, 18, 19, 21, only white blood cell count (WBC), serum C-reactive protein (CRP) and serum albumin ("targeted" lab) will be collected and fasting is not required for these labs.

Urine pregnancy testing for all woman of child-bearing potential will be conducted on-site prior to every dosing and must be negative to further treat the subject. A positive urine test must be confirmed with a serum pregnancy test.

Randomization via IRT and administration of study medication should be the last activity at Visit 2.

Venipuncture (i.e., safety laboratories, PK, anti-drug antibody [ADA]), should be the last procedure prior to study drug administration.

Follow Up Period and Trial Completion

For all randomized subjects termination of trial medication and trial completion must be recorded on the corresponding eCRFs.

Early Treatment and Trial Termination

Subjects who prematurely discontinue (PD) treatment prior to the planned [Appendix C](#) visit schedule will complete EOT visit procedures instead of the planned treatment period

visit. If study medication is discontinued, every effort should be made to have the subject continue in the trial and complete all of the follow remaining trial and follow up visits. If a subject cannot or will not continue in the trial, these subjects should be registered as withdrawn/discontinued in IRT. These subjects should be registered as withdrawn in IRT and return to the clinic for Week 188 Follow-Up visit 16 weeks after last dose of study medication.

Trial Completion

Subjects who finish the randomized treatment period will return to the clinic for Week 184 Follow-Up Visit and Week 188 Follow-Up Visit. Completion is defined as a subject having completed the Week 188 Follow-Up visit.

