5.5 Treatments

5.5.1 Treatments Administered

Subjects in each group will receive either 150 mg or 75 mg of risankizumab at Week 0, 4 and every 12 weeks after. All products will be supplied by BI.

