10. Collected for Substudy EP.

11. Subjects that terminate trial medication early will complete EOT Visit procedures instead of the planned treatment period visit and return for Week 188 Follow-up Visit, 16 weeks after last dose of study medication.
12. Vital Status should be collected for subjects leaving the study before the planned Week 188 Follow-up visit.

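### SAP 6.0 visit windows count from first dose only, so the follow-up visit of a subject who has left the trial can supply a Week 16 or Week 52 response, or help impute one

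*SAP*

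**What the plan says.** **Windows.** SAP 6.0 (Definition of Analysis Windows) states: "All time points and corresponding time windows are defined based on Rx Days". Rx Day 1 is the day of first dose. When a window holds several values, "If more than one assessment is included in a time window the assessment closest to the nominal day will be used". The only row for the Week 188 visit in SAP Table 1 is Days 1262 to 1282. SAP 10.1 admits efficacy data from the start of risankizumab onward and sets no limit after the last dose.

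**Follow-up of subjects who leave.** Under Protocol 5.1 (Early Treatment and Trial Termination), subjects who cannot or will not continue are registered as withdrawn and "return to the clinic for Week 188 Follow-Up visit 16 weeks after last dose of study medication". Appendix C, note 11, has early stoppers do the end-of-treatment (EOT) procedures in place of the next planned visit and then "return for Week 188 Follow-up Visit, 16 weeks after last dose of study medication".

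**Missing binary data.** Rule 1 in SAP 6.0 makes a missing visit a failure when no assessment follows it. Rule 2 reads: "If there are assessments at visits* before and after, only impute as success if both visits are successes; else impute as failure". Users of prohibited psoriasis medication "will be treated the same as those that discontinued from the trial", which is then explained as failure at visits after that medication starts. Protocol 8.1.9 has the same text.

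**The concern.** The visit is scheduled from the last dose but windowed from the first dose. For anyone who leaves early, the visit cannot reach the Week 188 row, so it falls in a treatment-visit window. There it counts as an ordinary on-schedule assessment, or as the later of the two visits that rule 2 needs.

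The sentence on prohibited medication presupposes that subjects who discontinue the trial are failures afterwards. No written rule does this for them: the operative wording covers prohibited medication only, and rules 1 and 2 act only on visits that are missing. A programmer who follows the SAP literally could therefore count a subject who has left the trial as a responder. Whether that happens would turn on attendance at one visit after withdrawal. The primary endpoints (Week 16) and the secondary endpoints (Weeks 16 and 52) are exposed.

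**Working it through.** **Inputs.** Dosing, from Protocol 5.5.1: "Subjects in each group will receive either 150 mg or 75 mg of risankizumab at Week 0, 4 and every 12 weeks after". Follow-up interval: 16 weeks × 7 = 112 days. Windows: SAP Table 1 and the DLQI window table.

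**Reproducing the plan's target days.** Target day = 7 × week + 1. This gives 113 for Week 16 (7 × 16 + 1) and 365 for Week 52 (7 × 52 + 1), as in Table 1. It matches 19 of the 22 post-baseline rows, including every row from Week 4 to Week 160. Weeks 172, 184 and 188 do not fit; that is a separate matter and is not used below. Table 1's own targets for Weeks 172 and 188 are 1275 − 1163 = 112 days apart, which agrees with the follow-up interval.

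**Placing the visit.** Follow-up day = last-dose day + 112.

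| Last dose | Last-dose day | Follow-up day | Table 1 window |
|---|---|---|---|
| Week 0 | 1 | 113 | Week 16 [100, 134], on target |
| Week 4 | 29 | 141 | Week 22 [135, 176] |
| Week 16 | 113 | 225 | Week 34 [219, 260] |
| Week 28 | 197 | 309 | Week 46 [303, 344] |
| Week 40 | 281 | 393 | Week 52 [345, 407] |
| Week 52 | 365 | 477 | Week 64 [408, 491] |

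Of the five possible last doses before Week 52, two put the visit directly in a Week 16 or Week 52 window.

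- **Week 0.** Day 113 is the target itself, so no value on another day can be nearer.
- **Week 40.** Day 393 is 393 − 365 = 28 days from target. An assessment anywhere from Day 345 to Day 392 is at most 27 days away and would be used instead. Day 393 therefore counts only if the EOT visit fell on Day 344 or earlier.
- **Week 4.** Suppose the subject responded at the visit before Week 16, has no value in [100, 134], and responds on Day 141. Without the Day 141 visit, rule 1 makes Week 16 a failure. With it, rule 2 makes Week 16 a success. If Week 12 is also missing, this requires reading rule 2 across two consecutive missing visits. If the visit is 7 days early, it falls on Day 134 and is itself the Week 16 value.

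**DLQI.** The windows are wider: Week 16 is [100, 239] and Week 52 is [240, 407]. Days 113, 141 and 225 fall in Week 16, and Days 309 and 393 fall in Week 52. A scheduled Day 113 value would displace Day 225.

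**Weight of one subject.** 1/4 = 25 points in an arm of 4; 1/8 = 12.5 points in a substudy of 8. The SAP plans 95% CIs for percentages without naming a method. With exact (Clopper-Pearson) limits, an assumption here, 4/4 (39.8 to 100) becomes 3/4 (19.4 to 99.4), and 8/8 (63.1 to 100) becomes 7/8 (47.3 to 99.7).

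**The case against.** **The text may already make discontinuers failures.** In Protocol 8.1.9 the sentence on prohibited medication is a footnote attached by asterisk to the visits named in both rules. The SAP keeps those asterisks but drops the mark on the note. This shows intent and is the best argument against the point. It does not settle it, because the explanatory clause names only the start of prohibited medication, and nothing in the window algorithm carries the intent out for other leavers.

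**Off-drug data are partly the design.** Protocol 5.4.1 asks subjects who stop drug to stay and complete all visits. This stands: those subjects keep their scheduled Week 16 and Week 52 visits. A reader might infer that any early stopper is affected, but the point reaches only subjects who leave the trial. Leavers who start prohibited psoriasis medication are already failures from then on.

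**The difference from a scheduled visit can be mild.** The scheduled Week 52 visit is itself 365 − 281 = 84 days (12 weeks) after the Week 40 dose, against 16 weeks here. At Week 16 the gap is larger: one dose 16 weeks earlier, against two doses with the last 12 weeks earlier.

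**LOCF.** A reader might infer that follow-up values will be carried into later treatment visits. SAP 6.0 limits LOCF to the same period, and the protocol separates treatment from follow-up. Because period is not defined, this is an ambiguity and not an established error.

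**Completion.** Protocol 5.1 says "Completion is defined as a subject having completed the Week 188 Follow-Up visit", and a reader might infer that a leaver who attends that visit becomes a completer. The documents do not support this. The sentence follows directly on the one about subjects who finish the randomized treatment period, leavers are registered as withdrawn, and SAP 8.0 counts completion at Week 28.

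**Collection.** Table 1 pools efficacy variables with laboratory tests, vital signs and local tolerability, and the Appendix C rows are not legible enough to confirm which efficacy measures are taken at follow-up. This limit stands.

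**Conclusion.** The point holds in a limited form. Followed literally, the SAP can use a post-withdrawal visit as the Week 16 value (last dose Week 0) or the Week 52 value (last dose Week 40, no assessment nearer Day 365). It can also use that visit to impute a missing Week 16 as success (last dose Week 4, success at the visit before). This conflicts with the premise, in both documents, that trial discontinuers are failures at later visits.

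The conclusion assumes that efficacy is assessed at that follow-up visit, as the Week 188 rows of Table 1 and the DLQI table imply, and that the leaver has not started prohibited psoriasis medication. Its effect depends on such withdrawals occurring, and the documents give no expected number.

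Each affected subject shifts a rate by 25 points in an arm of 4, or 12.5 points in a substudy of 8. A reader might infer that the primary result is invalid. That goes too far: no hypothesis test is planned, the rates are descriptive, and the routes are few. It remains a contradiction worth removing before database lock.

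**What to change.** In SAP 6.0:

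- (a) Assign the post-withdrawal follow-up visit to a separate follow-up row by days since last dose. Make it ineligible for treatment-visit windows and as the later visit in binary rule 2.
- (b) State that, in the NRI analysis, binary endpoints are failures at scheduled visits after the subject left the trial.
- (c) Define period in the LOCF rule so that follow-up values are not carried into treatment visits.
- (d) Present follow-up values separately.

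The cost is a few lines of text and programming. Response rates may come out slightly lower.

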8.1.3 Planned Analyses

No formal hypothesis testing is planned for this trial.

The analysis will be performed using SAS® (SAS Institute Inc., Cary, NC, USA).

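### The closest-to-nominal-day rule can drop an early-stop assessment held between visits, so LOCF may carry forward the value from before the worsening

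*SAP*

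**What the plan says.** SAP 6.0 (Definition of Analysis Windows) sorts efficacy assessments into windows by Rx day. Where two fall in the same window: "If more than one assessment is included in a time window the assessment closest to the nominal day will be used". Ties go to the later assessment, and the worse value is preferred only among same-day assessments. SAP Table 1 (PASI, JDA, PGA-GPP, CGI-GI, BSA) and the separate DLQI window table list scheduled weeks only. Neither has a row or an exception for an early EOT or premature-discontinuation (EOT/PD) assessment.

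The imputation rules follow in the same section.

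- **Continuous endpoints:** "The LOCF will use the last observed non-missing evaluation", taken from the preceding visit.
- **Binary endpoints:** a missing value is a failure if nothing is observed later. Otherwise: "If there are assessments at visits* before and after, only impute as success if both visits are successes; else impute as failure".
- **Prohibited psoriasis medication:** visits after its start are failures. This is stated for binary endpoints only. The same sentence puts these subjects on the same footing as subjects who left the trial.

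Protocol 5.1 says subjects who stop treatment early "will complete EOT visit procedures instead of the planned treatment period" visit. Protocol Appendix C, note 11, has them "return for Week 188 Follow-up Visit, 16 weeks after last dose of study medication". SAP 10.1 adds an as-observed analysis, which is secondary for continuous variables.

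**The concern.** The EOT assessment records the subject's state when treatment stopped. Protocol 5.2.3.2 and 5.4.1 provide for stopping because of worsening or adverse events, and neither is tied to a visit day, so some EOT assessments may fall between scheduled visits. If such an assessment shares a window with an earlier, better visit, the windowing rule removes it and LOCF may carry the better value forward. For subjects who stop because they are worse, the error favours the drug.

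The as-observed analysis uses the same windows, so it would not show the loss. Arms hold about four subjects, so a single subject matters.

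**Working it through.** **Inputs.** Target days and windows are from SAP Table 1 and the DLQI window table. (The SAP 6.0 text also gives Week 4 as Rx Day 28 and points to Protocol Appendix C for windows. I used the tables, which give Day 29 and explicit intervals.) Follow-up is 16 weeks (112 days) after the last dose. The documents give neither the frequency nor the timing of early stops. I assume an EOT is equally likely on any day between two visits.

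**1. Reproduce the windows.** Upper bound = midpoint of adjacent target days: (29+57)/2 = 43; (85+113)/2 = 99; (113+155)/2 = 134; (365+449)/2 = 407. All 21 boundaries from Week 4 to Week 188 match.

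**2. Days on which an EOT is discarded, visits on target.** Discarded days = upper bound − target day.

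| Gap | Days between visits | Discarded | Share |
|---|---|---|---|
| Weeks 4–16, each of 3 gaps | 27 | 14 | 51.9% |
| Weeks 16–52, each of 6 gaps | 41 | 21 | 51.2% |
| Weeks 52–160, each of 9 gaps | 83 | 42 | 50.6% |
| Weeks 160–172 (printed targets 1121 and 1163) | 41 | 21 | 51.2% |

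- To Week 52: (3×14 + 6×21)/(3×27 + 6×41) = 168/327 = 51.4%.
- To Week 160: (168 + 9×42)/(327 + 9×83) = 546/1074 = 50.8%.
- To Week 172: 567/1115 = 50.9%.

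An EOT before any Week 4 visit is always kept.

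**3. Visits off target.** I shifted both visits bounding a gap together, uniformly over ±3 or ±7 days.

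| Shift | To Week 16 | To Week 172 |
|---|---|---|
| ±3 days | 258/567 = 45.5% | 3741/7805 = 47.9% |
| ±7 days | 462/1215 = 38.0% | 7441/16725 = 44.5% |

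**4. DLQI.** The Week 16 window is [100, 239] with target 113. An EOT exactly at Week 22, 28 or 34 (Days 155, 197, 239) is 42, 84 or 126 days from target, so it loses to any attended Week 16 visit. This assumes DLQI is collected at an early EOT, which the table's Week 172 window suggests.

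**5. LOCF on windowed values.**

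- EOT on Day 92: 7 days from the Week 12 target, against 0 for an on-time visit, so it is dropped. The Week 12 value is carried to Week 16. Follow-up on Day 29 + 112 = 141 falls in the Week 22 window [135, 176] and ends the carry.
- EOT on Day 125, last dose Day 113: dropped. The Week 16 value is carried to Weeks 22 and 28, until follow-up on Day 113 + 112 = 225 (Week 34 window [219, 260]). For DLQI, Day 225 still lies in the Week 16 window, so a follow-up DLQI would be dropped too.

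**6. Week 16 response.** Take a subject who is a success through Week 12, has no prohibited medication, and last dosed on Day 29. The discontinuation clause is deliberately not applied here.

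| EOT failure | Later assessment | Week 16 |
|---|---|---|
| Day 92 | none | failure |
| Day 92 | Day 141, failure | failure |
| Day 92 | Day 141, success | imputed success |
| Day 105 | Day 141, success | observed failure (window [100, 134]) |

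If Week 16 is attended in its own right, its value is observed. The exposed EOT days are 30–43, 58–71 and 86–99.

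**7. Week 52**, for a subject next seen only at follow-up. Last dose Day 281 gives Day 393, inside [345, 407], so Week 52 is observed. Last dose Day 197 gives Day 309 (Week 46 window), so Week 52 is a failure. Neither case yields an imputed success.

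**8. Weight of one subject.** Eight per disease, "randomized in a 1:1 fashion in each group", gives about 4 per arm. One changed response is 1/4 = 25 percentage points. A carried value that is wrong by d moves the arm mean by d/4.

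**The case against.** A reader might infer that a subject who worsens and stops is generally turned into a Week 16 responder. The documents do not support that.

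- With no later assessment, or with a later failure, the SAP gives failure.
- The clause on prohibited medication uses subjects who left the trial as its reference case. Read naturally, their later visits are already failures, and a good follow-up visit cannot rescue Week 16. In Protocol 8.1.9 the clause is the footnote to the word visits in both binary rules.
- Subjects who stop only the drug are meant to keep attending, so Week 16 would normally be observed.
- A subject who starts a prohibited psoriasis medication is a failure from then on. Whether an increase in permitted background therapy counts as prohibited is not stated.

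A reader might also take 51% as the share of early stoppers affected. It is a share of possible days, and the Protocol describes the EOT as replacing a planned visit.

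Three further objections carry weight. The LOCF sentence could be read to include an EOT that lost its window. Every primary and secondary endpoint is binary, so LOCF touches only the other endpoints. And the study is descriptive: "No formal hypothesis testing is planned for this trial".

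These points narrow the concern but leave the LOCF part standing. The windowing text has no EOT exception. The LOCF wording points to the preceding visit without saying whether that means the windowed value. The prohibited-medication rule gives continuous endpoints no protection. For DLQI, even an on-schedule EOT is lost.

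**Conclusion.** The concern holds for the continuous summaries. With on-time visits, about 51% of the possible between-visit EOT days lead to discard, and 38% to 48% if visits are off target by up to 3 or 7 days. For DLQI, EOTs at Weeks 22, 28 and 34 are also lost when Week 16 was attended. If LOCF runs on windowed values, PASI, JDA, BSA and DLQI carry the pre-worsening value until a later visit is observed. The number of such EOTs is not given, so the size of any bias cannot be stated.

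For the primary endpoint the risk is narrow. It needs all of these together: success at the last kept visit, a failing EOT on one of the exposed days, Week 16 missing, a later success, no prohibited psoriasis medication, and a reading under which the discontinuation clause does not make later visits failures. If it happened, one subject would move an arm of about four by 25 points. The cases checked did not extend this path to Week 52. This is worth correcting in the SAP, but it does not undermine the primary analysis.

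**What to change.** Add two statements to SAP 6.0:

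1. LOCF starts from the chronologically last non-missing assessment, including an EOT/PD assessment that was not selected for its window.
2. In the second binary rule, the assessment before the gap is the chronologically nearest one, including EOT/PD. A follow-up visit after treatment discontinuation cannot serve as the assessment after it to impute success.

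Keep the closest-to-nominal rule for the value reported at each visit. A separate EOT/PD row in the efficacy tables is optional.

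With these statements no EOT value is lost to LOCF, and the Day 92 / Day 141 subject becomes a Week 16 failure whichever way the discontinuation clause is read. The cost is a few sentences and minor programming, with no new data. Mean changes, and rarely a response rate, may look slightly less favourable.
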